13.0 Risks to Participants

13.1 Foreseeable Risks:

Our study procedures involve minimal risk. Patients may experience discomfort from quitting or attempting to quit smoking. Use of NRT has led to skin irritation in the case of the patch and occasionally to nausea in the case of the lozenge or patch. We will provide instructions in correct use of NRT and will advise patients to discontinue use in the event of significant nausea or discomfort.

Patients will need to make in-person visits as well as be available for phone counseling sessions. Both of these could pose an inconvenience and we will do our best to accommodate patients' schedules and needs.

In addition to the above mentioned minimal risks, we will also store all study related data in secured locations separately from personal identifiers to ensure information remains strictly confidential.

14.0 Potential Benefits to Participants

14.1 Potential Benefits:

The potential benefits to participation in our study include all of the benefits related to a reduction in smoking or quitting smoking, including improving cardiovascular health.

15.0 Statistical Considerations

15.1 Data Analysis Plan:

Feasibility analyses (e.g. recruitment rate, retention rate) and acceptability analyses (e.g., satisfaction scores, sessions attended, uptake of NRT) will be primarily descriptive. Given the limited number of participants, primary and secondary outcome analyses will be exploratory and will be used for effect size estimates for a potential larger future trial.

15.2 Power Analysis:

Although we are not powered to detect differences in abstinence, the current study will provide a necessary demonstration of the feasibility of our approach.

15.3 Statistical Analysis:

All analyses will be conducted on the intent to treat sample, with all randomized participants included in the analysis. We will estimate the effect of the intervention on smoking cessation (biochemically verified 7-day point prevalence abstinence) over 6 months using a single repeated measures regression model implemented with generalized estimating equations (GEE) and robust standard errors. Specifically, we will regress smoking status on intervention group and potential covariates using binomial errors, a logit link function, and a working unstructured correlation to accommodate within-subject correlation. For continuous secondary outcomes we will use linear regression models.

15.4 Data Integrity:

All study staffed will be trained on how to collect and store data. Data quality will be evaluated by study staff through review and assessment of gathered data to ensure completeness. Data will be kept in locked files or on a secure server, to both of which only authorized study personnel will have access. All identifying data will be stored separately.

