3.0 Study Endpoints/Events/Outcomes

3.1 Primary Endpoint/Event/Outcome:

The primary outcome of our study is to determine the proportion of patients in the intervention and control conditions who achieve 7-day point prevalence abstinence at 8 weeks and 6 months after enrollment

3.2 Secondary Endpoint(s)/Event(s)/Outcome(s):

The secondary outcome of our study is to determine the proportion of patients in the intervention and control condition who achieve continuous abstinence, reduced number of cigarettes per day, and self-reported minimum 24 hour quit attempts.

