4.2 Biosafety: N/A

4.3 Stem Cells: N/A

5.0 Procedures Involved

5.1 Study Design:

This is a randomized clinical trial that will enroll patients with documented SMI (ICD-10 codes) including schizophrenia, any other psychotic disorder, bipolar I and II disorder, and/or recurrent/chronic major depressive disorder into either a counseling intensive smoking cessation program or the control group.

5.2 Study Procedures:

This intervention is tailored to the needs of SMI smokers including addressing barriers to quitting and the need for continued supportive contact. Following is an outline of the study procedures:

Baseline assessment

Trained study staff will:

- Conduct informed consent
- Collect demographic and smoking history information along with current interest in quitting, readiness to quit, confidence in ability to quit, and nicotine dependence. We also will include mood, general psychiatric health, and quality of life questionnaires. (SMI Smokers BL Interview V1.1, SMI Smokers BL Self Report V1.1)
- Collect the name and phone number of an additional contact. Study staff will call the contact in the case of an emergency with the participant or if staff are unable to reach the participant for study visits. Staff will explain the two reasons for needing the additional contact person to the participant during the baseline visit.
- Randomize participants: prior to the baseline visit, we will complete a 1 to 1 non-stratified randomization. The randomization results will be put in envelopes to be opened during the baseline visit, determining if a participant will be allocated to the intervention or the control group.
- Conduct or schedule session one with those in the intervention group
- Distribute materials/resources to all participants.

Follow up assessments:

- Conducted at 8 weeks and 6 months post baseline assessment. (SMI Smokers 8 Week Interview V1.0, SMI Smokers 6 Month Interview V1.0,

and SMI Smokers 8W 6M Self Report V1.0, Study Satisfaction Survey V1.0 will be administered only at the 6 month assessment and only to participants in the Intervention group).

- Conducted in person when possible, but a phone option will be available.
- Measures will include current smoking status, quit attempts, self-reported number of cigarettes per day for those who currently are smoking, and interest and confidence in quitting/continued abstinence.
- Reported 7-day abstinence at 8 weeks and 6 months will be validated by an expired carbon monoxide sample.

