10.0 Local Number of Participants

10.1 Local Number of Participants to be Consented:

We plan to recruit 60 participants for the study. However, we are requesting permission to enroll up to 80 participants to allow for early dropouts and inability to reach participants following initial enrollment in the study.

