Department of Psychiatry. If study staff are contacted directly by a patient in response to a poster, we will have a two-step process for verifying their mental health diagnosis. Step one will be to look for their name on the list received from the CRA. If they are not on the list, [name], an Assistant Professor and licensed clinical psychologist within the Department of Psychiatry who is Co-I on this study and has legitimate access to patients' medical records, will verify diagnosis.

After the screening process is complete:

Those who are interested and who meet initial eligibility criteria will be invited to the ECRC study site for further assessment and enrollment in the study. We plan to recruit a minimum of 60 participants with close to equal distribution from HCMC and UMN clinics. During the first in person visit, participants will be randomly allocated to the intervention or control group with approximately 30 in each.

11.2 Identification of Potential Participants:

We may be hanging flyers in the HCMC and UMN psychiatric clinics which contain study information. Patients who are interested in the study will then be able to reach out to study staff to get more information.

At HCMC, a chart review of patients attending smoking cessation or psychiatric clinics will be used to identify potential participants. Letters that include a brief description of the study, information about opting out of the recruitment phone call, and an HCMC study phone number will be sent to patients. HCMC medical and psychiatric providers may also refer their patients to the study.

UMN Department of Psychiatry maintains a database of patients who have agreed to be contacted about research studies. The Clinical Research Advocate will be using this database to find patients interested in being participants and will then run a query of the database to find patients who meet our minimum requirements to be screened.

11.3 Recruitment Materials:

In addition to the proactive methods described above, we may also place flyers describing the study and containing study contact information within the clinics so that patients may self-identify for the study. Study recruitment flyers are attached in the ETHOS recruitment section.

11.4 Payment:

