12.0 Withdrawal of Participants

12.1 Withdrawal Circumstances:

Because we are using an intention-to-treat paradigm, subjects will be encouraged to continue their participation even if they are unsuccessful in quitting or making significant reductions in smoking. Participants may choose to withdraw from the study at any time without penalty. The PI and Co-PI may withdraw a patient from the study without their consent if that patient has an active psychotic episode or is hospitalized due to suicidal ideation or suicidal behavior. If this happens, trained study staff will have a conversation with the participant explaining the reasons for their withdrawal from the study.

12.2 Withdrawal Procedures:

If a participant withdraws from the study, no new data will be collected on that participant.

12.3 Termination Procedures:

If a participant is terminated from the study, no new data will be collected on that participant.

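### Does Section 15.3 need a written coding rule for missing outcomes before its all-randomized GEE can be run?

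*Combined protocol and SAP*

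**What the plan says.** Section 15.3 sets the analysis population: "All analyses will be conducted on the intent to treat sample, with all randomized participants included in the analysis". The model is a single repeated-measures GEE with a logit link and robust standard errors, and its outcome is biochemically verified abstinence over 6 months. Section 3.1 sets out to "determine the proportion of patients in the intervention and control conditions who achieve 7-day point prevalence abstinence", at 8 weeks and at 6 months.

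On follow-up visits, Section 5.2 says: "Conducted in person when possible, but a phone option will be available". On verification it says: "Reported 7-day abstinence at 8 weeks and 6 months will be validated by an expired carbon monoxide sample".

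The plan expects some loss. Section 10.1 puts the recruitment goal at 60 and adds: "we are requesting permission to enroll up to 80 participants to allow for early dropouts and inability to reach participants following initial enrollment". Section 11.1 places allocation early: "During the first in person visit, participants will be randomly allocated to the intervention or control group with approximately 30 in each". Section 12.2 says: "If a participant withdraws from the study, no new data will be collected on that participant". Section 12.3 says: "If a participant is terminated from the study, no new data will be collected on that participant".

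Section 15.1 calls the outcome analyses exploratory, meant to supply effect sizes for a possible larger trial, and lists retention among the descriptive results. Section 15.2 says that the study is not powered for abstinence.

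**The concern.** Section 15.3 promises that everyone randomized is analysed, yet the one model it names uses only outcome rows that exist. Someone seen at one of the two visits stays in the fit. Someone seen at neither drops out of it without notice. Because envelopes are opened at the baseline visit, an early dropout is normally already randomized, and after withdrawal nothing more is collected. A baseline row would not help: every participant is a daily smoker at entry (Section 8.1), so it carries no information on abstinence.

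Two readings then seem open: omit people with no outcome, or count them as not abstinent. They give different proportions per arm, and different odds ratios when loss differs by arm. Differential loss is plausible, because the intervention arm has an in-person session and at least nine calls (six, then a minimum of three), while controls have assessments, information, a helpline referral and letters. Phone follow-up raises a smaller version of the question: how to treat a report of abstinence without a CO sample. Since the estimates may feed a larger trial, the worry is a rule chosen after the results are known.

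**Working it through.** The plan gives no abstinence rate, loss rate, power or alpha, so there is no stated figure to reproduce.

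**Inputs.** From the documents: goal 60 and ceiling 80 (10.1); 1:1 allocation (5.2), hence 40 per arm at the ceiling; two outcome visits (5.2). The largest loss that 10.1 could be read to cover is (80 − 60)/80 = 25%. That is a permission ceiling, not an expected rate, and 10.1 does not say that those 20 people would lack both outcomes. Abstainer counts and the split of losses by arm are assumed throughout.

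**Equal loss: 10 per arm, 6 versus 3 verified abstainers.**
- Omitted: 6/30 = 20% versus 3/30 = 10%; OR = (6/24)/(3/27) = 2.25.
- Counted as not abstinent: 6/40 = 15% versus 3/40 = 7.5%; OR = (6/34)/(3/37) = 2.18.

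The rates fall by a quarter and the odds ratio barely moves. For planning a later trial, take n per arm = [1.96·√(2p̄(1−p̄)) + 0.84·√(p1(1−p1) + p2(1−p2))]² / (p1−p2)², assuming 80% power and two-sided 5%. This gives 199 for 20% versus 10%, and 278 for 15% versus 7.5%. The two are in different units: 199 counts people with an outcome, while 278 counts people randomized, because its rates already contain the loss. At the same 25% loss, 199/0.75 = 265.3, so 266 must be randomized. Like for like it is 266 versus 278, and 278/266 = 1.045, a difference of about 5%.

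**Unequal loss, no true effect (10% abstinent in each arm of 40).** Each cell is an odds ratio, intervention versus control.

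| Lost (int. / control) | All lost smoke: omitted | All lost smoke: counted | Loss unrelated to smoking: omitted | Loss unrelated to smoking: counted |
|---|---|---|---|---|
| 8 / 12 | (4/28)/(4/24) = 0.86 | (4/36)/(4/36) = 1.00 | 1.00 | 0.08 vs 0.07: 0.0870/0.0753 = 1.16 |
| 5 / 15 | (4/31)/(4/21) = 0.68 | 1.00 | 1.00 | 0.0875 vs 0.0625: 0.0959/0.0667 = 1.44 |

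In the 5 / 15 row with all lost smoking, the control rate is 4/25 = 16% if the lost are omitted and 4/40 = 10% if they are counted, a relative fall of 37.5%. A single rate can therefore move by more than a quarter when loss is lopsided.

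**The planned type of model.** A two-visit logit GEE was fitted with robust errors, one within-person correlation and arm only, with 4 abstainers per arm per visit (2 of them at both visits) and 5 versus 15 lost at both visits. On available cases it uses 60 of 80 people: OR 0.68 (95% CI 0.19 to 2.38). With everyone coded it uses all 80: OR 1.00 (0.29 to 3.46).

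**Sampling error.** At 4/40 versus 4/40, SE(log OR) = √(2(1/4 + 1/36)) = 0.745, so the 95% interval is exp(±1.96 × 0.745) = 0.23 to 4.31. Every odds ratio above lies inside it.

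**Unverified reports.** Suppose one of 4 intervention reports has no CO sample, against 4 of 40 in control. As not abstinent, OR = (3/37)/(4/36) = 0.73; omitted, (3/36)/(4/36) = 0.75. Accepting the self-report gives 1.00, but self-report alone is not the outcome that 15.3 names.

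**The text side by side.** Dropping people with no outcome is a software default. The plan does not ask for it, and the 15.3 sentence rules it out. The same sentence makes the number randomized the denominator, whatever that number turns out to be; 30 and 40 per arm are a recruitment target and a ceiling. The outcome is verified abstinence, so a person with no visit or no CO sample has not met it.

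**The case for a change.** The strongest reply is that counting the unseen as not abstinent is a convention, not something the document says. Some analysts read intention-to-treat as analysed in the arm assigned, and would fit the GEE to available rows without feeling that they had broken the plan. With more contact in one arm and withdrawal possible after psychiatric events, the missingness may not be random. One sentence written beforehand would cost almost nothing and would remove a choice that could otherwise be made with the data in view.

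Part of this stands. No section states the coding, and a report of the trial should say what was done and show the numbers missing and unverified by arm and visit. But 15.3 goes further than assignment: it says that everyone randomized is in the analysis, which an available-case fit does not deliver. Nor would a written rule make the estimate safer. Each candidate has its own bias (0.68 or 1.44 in the same 5 / 15 example), and which one applies depends on why people leave, which cannot be known beforehand. Because retention is already a planned result, a reader given abstainer counts, numbers seen and numbers randomized can compute the simple proportions both ways.

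**Conclusion.** No change is needed. This is missing detail that an analyst following Section 15.3 fills sensibly: all randomized participants form the denominator, and anyone without verified abstinence is counted as not abstinent. The text contains no stated rule that gives a wrong result, and no alternative is better in every case.

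The size is small for this trial's purpose. With equal loss the odds ratio goes from 2.25 to 2.18, and the planning number differs by about 5% on a common footing. With lopsided loss the shift is larger (0.68 versus 1.00, or 1.00 versus 1.44), but it stays well inside sampling error of 0.23 to 4.31. These figures rest on assumed abstinence counts, assumed splits by arm, and loss at the full 25% that the enrollment ceiling could cover. The conclusion also rests on the analyses being exploratory, as 15.1 and 15.2 state; a confirmatory trial would need the rule in writing.

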1.0 Objectives

1.1 Purpose:

This is a pilot study to assess the following research aims:

- 1) **Is our approach is feasible?** Can we recruit smokers with SMI, deliver counseling and NRT, and keep participants engaged over the six months of intervention? Can we minimize attrition and loss to follow up?
- 2) **Are our proposed treatments acceptable?** How much counseling will we be able to deliver? How many participants will adhere to recommended NRT? Will participants utilize options for re-treatment after relapse or failing to initiate a quit/reduction attempt?
- 3) **How do 7-day abstinence outcomes** (and continuous abstinence, quit attempts, and reduced smoking) **compare between intervention and control conditions at 1- and 6-month follow-ups?**

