4.0 Study Intervention(s)/Investigational Agent(s)

4.1 Description:

This randomized trial will include in-person meetings and phone counseling sessions with participants. We will seek to deliver treatment that optimally follows current guidelines, provides for substantial counseling support, includes an option for NRT, and keeps patients engaged in quitting.

Drug/Device Handling:

We will be using different types of NRT in this study including lozenge and patches. Only study staff who have been trained to follow standard operating procedures for handling and distributing the NRT drugs used in this study will have access to them. These NRT drugs are currently FDA approved, on the market, over-the-counter medicines that do not require a doctor or pharmacist for distribution. All NRT drugs will be kept in the locked Drug Supply Room at the ECRC. The study coordinator will maintain a Drug Accountability Record of the purchase and distribution of all NRT drugs.

Patients will be offered the nicotine patch (dose based on number of cigarettes per day) and/or the nicotine lozenge (2 or 4 mg if less or greater than 30 minutes to first cigarette in the morning respectively) depending on participant preference and how much they are smoking based on FDA guidelines for use. We will follow FDA guidelines for the length of time a participant should use their NRT, anywhere between 8 and 12 weeks, depending on cigarette use, addiction level, and type of NRT. Participants will receive a four-week supply of NRT during the baseline visit. If participants are using and want to continue using NRT,

the remainder of their supply will be distributed to them at 4 weeks. We will either mail subsequent NRT in puncture resistant packaging to the participants or participants come to the ECRC to pick up their remaining supply.

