The intervention group activities include the following:

Session 1:

- 1 hour in person visit
- Will include population specific information about smoking and mental illness
- Counselor will provide a strong and personalized recommendation to quit
- The remainder of Session 1 will be guided by current clinical practice guidelines and the National Cancer Institute's Clearing the Air patient workbook
 - The counselor will cover: past attempts to quit (reframing these as learning opportunities), and education on the risks of smoking and benefits of quitting both in general and for SMI patients.
 - Emphasis will be placed upon personal reasons for quitting or reducing number of cigarettes, especially those that are intrinsic
 - The counselor will discuss coping strategies and will focus on identifying strategies that are appropriate for the individual patient.
 - The counselor will provide tips for how to elicit support and for managing cravings
 - The counselor will address planning for behavior change including preparation for a quit date when applicable and anticipating challenging situations
- For those patients who initially choose to reduce rather than quit, the focus will be on reduction strategies including substituting NRT lozenge for individual cigarettes
- Patients who want to quit will be offered a nicotine patch and/or the nicotine lozenge.
- The counselor will review correct placement and/or use.
- Counselor also will address the efficacy and safety of nicotine replacement

Follow up counseling calls:

- Counselors will make 6 calls over 8 weeks after initial in person session.
- There will be assessments of current smoking status, NRT use and side

effects, and motivation to continue/restart quitting/reduction plan. NRT use will be encouraged.

- For those who have discontinued use or who have encountered problems with NRT, the counselor will review the patient's experience and consider alternatives including advice to try a different form of NRT
- If the patient is abstinent, the counselor will reinforce their success, discuss any times since the previous session when the participant struggled with cravings, will review strategies for managing triggers and cravings, and problem solve upcoming challenges to continued abstinence.

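### Section 15.3 plans one intervention effect pooled over 6 months, so no between-arm effect with a confidence interval is planned at 8 weeks or at 6 months, the two time points of the primary outcome

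*Combined protocol and SAP*

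**What the plan says.** Section 3.1 states the primary outcome as follows: "determine the proportion of patients in the intervention and control conditions who achieve 7-day point prevalence abstinence at 8 weeks and 6 months", both counted from enrollment. Section 5.2 schedules the carbon monoxide check of reported abstinence at the same two visits. Aim 3 in section 1.1 asks how abstinence outcomes "compare between intervention and control conditions at 1- and 6-month follow-ups".

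Section 15.3 plans to estimate the intervention effect on verified abstinence "over 6 months using a single repeated measures regression model", fitted by GEE with robust standard errors and an unstructured working correlation. The regression is specified as "we will regress smoking status on intervention group and potential covariates using binomial errors, a logit link function". The possible covariates are not listed. No visit term, group-by-visit term, visit-specific contrast or model per visit appears anywhere in the document.

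On the use of the results, section 15.1 says that "primary and secondary outcome analyses will be exploratory and will be used for effect size estimates for a potential larger future trial", and section 15.2 says "we are not powered to detect differences in abstinence".

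**The concern.** The outcome is defined at two visits, but the model returns one effect for both. If the effect differs between 8 weeks and 6 months, the single odds ratio describes neither visit. A later trial is usually sized on one stated time point, so its planner needs the effect and its uncertainty at that visit. The planner could compute point estimates from the proportions promised in section 3.1, but section 15.3 plans no interval for them.

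The documents do not settle whether the effect is constant. Delivery differs between the two periods. In the first, "Counselors will make 6 calls over 8 weeks after initial in person session", with nicotine replacement used for "anywhere between 8 and 12 weeks". In the second, section 5.2 provides at least 3 calls, text messages for those who agree, and up to six calls in new rounds for those who start another quit or reduction attempt. The effect could fade, hold or grow.

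**Working it through.** The plan states no abstinence rates, effect size or sample-size calculation, so there is no figure to reproduce. From the documents: two visits (3.1, 5.2) and about 30 participants per arm (11.1). All abstinence rates and within-person correlations below are assumptions.

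**1. What the model can return.** With G for group and V for visit, logit P(abstinent) = b0 + b1·G gives a log odds ratio of b1 at both visits. Adding b2·V still leaves b1 at both. Adding b3·G·V gives b1 at 8 weeks and b1 + b3 at 6 months. Reading the unlisted covariates as including visit therefore does not supply visit-specific effects.

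**2. Single against visit-specific odds ratios.** With complete data, the group-only odds ratio is that of the visit-mean proportions. For the modest gap: (0.20 + 0.15)/2 = 0.175 v 0.10 gives (0.175/0.825)/(0.10/0.90) = 1.91. The column with a visit main effect solves the GEE equations at the assumed means for working correlations 0 to 0.5.

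| Intervention v control (8 weeks/6 months) | OR, 8 weeks | OR, 6 months | Single OR | Single OR with visit main effect |
|---|---|---|---|---|
| Constant: 20/20% v 10/10% | 2.25 | 2.25 | 2.25 | 2.25 |
| Both arms decline: 25/15% v 10/5% | 3.00 | 3.35 | 3.08 | 3.09 to 3.13 |
| Modest gap: 20/15% v 10/10% | 2.25 | 1.59 | 1.91 | 1.91 to 1.94 |
| Large gap: 30/12% v 10/10% | 3.86 | 1.23 | 2.39 | 2.43 to 2.81 |

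Reversing the modest gap (15/20% v 10/10%) swaps the two visit figures and leaves the single value unchanged.

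**3. Consequence for planning, modest gap.** n per arm = [1.96·√(2p̄(1−p̄)) + 0.8416·√(p1(1−p1) + p2(1−p2))]² / (p1−p2)², for 80% power and two-sided 0.05.
- 20% v 10%: (0.990 + 0.421)²/0.01 gives 199.
- 15% v 10%: (0.917 + 0.392)²/0.0025 gives 686.
- 17.5% v 10%, the blend: 330.

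**4. Precision at 30 per arm.** The standard error of the log odds ratio is the square root of the summed reciprocals of the four expected counts.
- 20% v 10%: √(1/6 + 1/24 + 1/3 + 1/27) = 0.761, so OR 2.25 (95% CI 0.51 to 9.99).
- 15% v 10%: √(1/4.5 + 1/25.5 + 1/3 + 1/27) = 0.795, so OR 1.59 (0.33 to 7.54).
- Single OR at within-person correlation 0.5: 1.91 (0.51 to 7.11).

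**5. Power to detect a difference between visits, large gap.** The ratio of visit odds ratios is 3.86/1.23 = 3.14, with log 1.145. Its variance sums, over arms, [1/(p8q8) + 1/(p6q6) − 2ρ/√(p8q8·p6q6)]/30, where p8 and p6 are the arm's abstinence rates at 8 weeks and 6 months and q = 1 − p.
- ρ = 0: SE 1.102, z = 1.04, power about 18%.
- ρ = 0.5: SE 0.788, z = 1.45, power about 31%.

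**6. Empty cells.** The chance that at least one arm of 30 has no abstinent participant at a given visit:
- 20% v 10%: 1 − (1 − 0.80³⁰)(1 − 0.90³⁰) = 4%.
- 15% v 10%: 1 − (1 − 0.85³⁰)(1 − 0.90³⁰) = 5%.
- 10% v 5%: 1 − (1 − 0.90³⁰)(1 − 0.95³⁰) = 1 − 0.958 × 0.785 = 25%. At either visit, if visits were independent, 1 − 0.752² = 43%; positive correlation lowers this.

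The risk difference survives an empty cell: for 3/30 v 0/30 the Newcombe interval is 10 points (−3.1 to 25.6).

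**The case against.** The strongest reply is that little is lost. Section 3.1 promises the proportions by arm and visit. With complete data and no covariates, the group-by-visit model is saturated, so its odds ratios are those of the four proportions, and a reader with denominators could compute the intervals. This stands as a reason for low weight. It does not cover incomplete data without reported denominators, or a covariate-adjusted effect.

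Second, an average effect over 6 months is a legitimate target that uses both visits and is estimated somewhat more precisely. That also stands, and a reader should not infer that the pooled model is invalid. With a constant effect it gives the right value at both visits, and when both arms decline together 3.08 against 3.00 and 3.35 is a negligible gap.

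Third, sampling error dwarfs the choice of model: the 6-month interval of 0.33 to 7.54 is far wider than the distance from 1.59 to 1.91. This is true, and the planning sizes in step 3 only illustrate how the estimates might be carried forward. A reader might go further and infer, from a pooled interval that covers both visit odds ratios, that the data could not show any difference between visits. That does not follow. The difference is judged by the interaction, and power for it is low but not nil: about 18% to 31% in the large-gap case.

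Finally, aim 3 supports a comparison at each follow-up but names 1 and 6 months. It cannot be cited for the 8-week visit until it is reconciled with sections 3.1 and 5.2.

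**Conclusion.** The point holds as a minor mismatch between outcome and model. Followed as written, section 15.3 gives one common odds ratio and no between-arm effect with an interval at either time point in section 3.1. No error rate, sample size or decision rule depends on it.

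The size depends on assumed rates: nothing if the effect is constant, and in the modest-gap case a single 1.91 in place of 2.25 and 1.59, or 330 per arm in place of 199 and 686. Two stronger readings are not supported. One is that results by visit would be absent altogether; section 3.1 commits to the proportions. The other is that the pooled figure would mislead in a known direction; the documents do not say whether the effect fades or grows.

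**What to change.** In section 15.3:
- Add visit (8 weeks, 6 months) and group-by-visit to the GEE.
- At both visits, in all cases, report the risk difference between arms with a score-based 95% CI (for example Newcombe), beside the observed proportions and denominators. Using one measure throughout keeps the visits on the same scale even if a cell is empty.
- Report visit-specific odds ratios with 95% CIs from the GEE where they can be estimated.
- Keep the pooled odds ratio, labelled as a visit-averaged effect over 6 months.

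In section 1.1, reconcile the follow-up times in aim 3 with sections 3.1 and 5.2.

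The cost is wording only, with no new data. The downsides are the wide visit-specific intervals in step 4 and the chance that the interaction model cannot be estimated when an arm has no abstinent participants at a visit (step 6). The report should also say that power to detect a difference between visits is low, so differing visit estimates are not read as evidence of a changing effect.
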